8.2. Safety Analyses

8.2.1. Secondary Safety Analyses

8.2.1.1. Overview of Planned Secondary Safety Analyses

Table 8 provides an overview of the planned secondary safety analyses.

Table 8 Overview of Planned Secondary Safety Analyses

Endpoint	Analysis Population	Absolute						Change from Baseline								
		Stats Analysis			Summary		Individual		Stats Analysis			Summary		Individual		
		T	F	L	T	F	F	L	T	F	L	T	F	F	L	
Blood Pressure																
SBP, DBP and MAP changes from Baseline ^{1,2}	ITT				Y	Y				Y			Y	Y		
Number of BP exacerbation events per 100 patient years ²	ITT	Y			Y											
Subjects experiencing at least one BP exacerbation event during study ²	ITT	Y			Y											

NOTES :

- T = Table, F = Figure, L = Listing, Y = Yes display generated.
- Stats Analysis = Represents TFL related to any formal statistical analyses (i.e. modelling) conducted.
- Summary = Represents TFL related to any summaries (i.e. descriptive statistics) of the observed raw data.
- Individual = Represents FL related to any displays of individual subject observed raw data.

^[1] Analysis will be performed using all available (on and off treatment) BP values.

^[2] Analysis will be performed using on-treatment BP values only.

8.2.1.2. Planned Secondary Safety Statistical Analyses

Secondary Safety Statistical Analyses: Blood Pressure	
Endpoint(s)	
•	Change from baseline in SBP, DBP and MAP at Week 52 and at end of treatment
•	Number of BP exacerbation events per 100 patient years
•	N (%) of subjects with at least one BP exacerbation event during study

Secondary Safety Statistical Analyses: Blood Pressure
Model Specification

 • The difference in change from baseline in BP (SBP, DBP, and MAP) at Week 52 will be analyzed with a mixed model repeated measures (MMRM) approach with an unstructured covariance matrix to compare the difference in means between arms. The models will be fitted to scheduled BP data collected after baseline up to Week 52. Models will be run two times: 
 ○ On-treatment BP values only, excluding values collected during the stabilization period (Randomization date + 1 day to <Week 28). ○ On-treatment BP values only, including values collected during the stabilization period. 
The models will include factors for treatment, time, prognostic randomization stratification factors (see Section 0), baseline BP parameter and the baseline BP parameter by time and treatment by time interaction terms. Analyses will be done with the MIXED procedure in SAS, using the Kenward-Roger option to estimate denominator degrees of freedom and standard errors. For analyses using on- and off-treatment values, subjects who withdraw from the study before Week 52 are considered to be missing at random and in the analysis using on-treatment values only, subjects who permanently discontinue randomized treatment before Week 52 are assumed to be missing at random.
 • The difference in change from baseline in BP (SBP, DBP, and MAP) at the derived end of treatment (see Section 10.6.4) will be analyzed with an ANCOVA model including terms for treatment, prognostic randomization stratification factors (see Section 0) and the corresponding baseline BP parameter. This analysis will be performed using on-treatment BP values only. • The number of on-treatment BP exacerbation events per 100 patient years will be calculated (see Section 10.6.4). Confidence intervals for the rate per 100 patient years will also be reported. For within group rates and the ratio of model estimated exacerbation rates,, the point estimates, two-sided 95% confidence intervals, and one-sided p-value for the treatment group comparison will be obtained using a negative binomial model with treatment and the prognostic randomization strata as covariates and the logarithm of time on-treatment as an offset variable.
Model Results Presentation

 • BP parameter values (SBP, DBP, and MAP) will be summarized using mean, standard deviation, minimum, P25, median, P75, and maximum at each visit by treatment group. In addition to scheduled visits, the derived baseline value and end of treatment values will be summarized (see Section 10.6.4). Summaries of on-treatment BP values only and on- and off-treatment BP values together will be produced. A summary of on-treatment BP values by baseline dialysis type will be produced. On-treatment BP parameter values will be plotted by visit using a line plot. • BP parameter change from baseline values (SBP, DBP, and MAP) will be summarized using mean, standard deviation, minimum, P25, median, P75, and maximum at each post-baseline visit by treatment group. In addition to scheduled visits, the derivedend of treatment values will be summarized (see Section 10.6.4). Summaries of on-treatment BP values only and on- and off-treatment BP values together will be produced. A summary of change from baseline in on-treatment BP parameter values by baseline dialysis type will be produced. On-treatment BP parameter change from baseline values will be plotted by visit using a line plot.

Secondary Safety Statistical Analyses: Blood Pressure

 • For the MMRM analyses of change from baseline in BP parameters to Week 52, an LSMEANS statement will provide adjusted treatment group means and standard errors and a point estimate and two-sided 95% confidence interval for the adjusted mean treatment difference (daprodustat - darbepoetin alfa) and a one-sided superiority p-value for this test. • For the ANCOVA analyses of change from baseline in BP parameters to the derived end of treatment, the adjusted mean estimates and standard errors by treatment group, adjusted mean difference, two-sided 95% CI and one-sided superiority p-value for the difference in BP parameter between the daprodustat and darbepoetin alfa arms from the ANCOVA model will be presented. The number of subjects contributing to the analysis and the associated mean and standard deviation of the baseline and end of treatment values will also be displayed with the results of the ANCOVA model. • The model estimated on-treatment BP exacerbation rates per 100 patient years and associated 95% confidence intervals will be provided by treatment group. The ratio of model estimated on-treatment BP exacerbation rates and associated two-sided 95% confidence interval and one-sided p-value will also be provided for the comparison of daprodustat vs. darbepoetin alfa. • On-treatment BP exacerbations will be summarized as follows: The number and percent of subjects with 0, 1, 2, 3, 4, 5 and >5 on-treatment BP exacerbations will be provided by treatment group. Additionally, the number and percent of subjects with on-treatment BP exacerbations and number of on-treatment BP exacerbation events will be provided by treatment group, in total and by BP exacerbation type (see Section 10.6.4). The total treatment exposure in years and overall on-treatment BP exacerbation rate per 100 PY will be provided by treatment group. 
 ○ The BP exacerbation summary above will be repeated for the following groups and BP values: 
 ▪ All subjects, on-treatment post-dialysis BP values only ▪ All subjects, on-treatment pre-dialysis BP values only ▪ Hemodialysis subjects, all on-treatment BP values ▪ Hemodialysis subjects, on-treatment post-dialysis BP values only ▪ Peritoneal dialysis subjects, on-treatment post-dialysis BP values only
Model Results Interpretation

 • One-sided p-values will be compared to 0.025 to assess nominal significance.

8.2.2. Exploratory Safety Analyses

8.2.2.1. Overview of Planned Exploratory Safety Analyses

Table 9 provides an overview of the planned exploratory safety analyses.

CONFIDENTIAL

201410

Table 9 Overview of Planned Exploratory Safety Analyses

Endpoint	Analysis Population	Absolute				Change from Baseline			
		Summary		Individual		Summary		Individual	
		T	F	F	L	T	F	F	L
BP and BP Medication Changes									
SBP, DBP and MAP by visit	ITT	Included with BP secondary analyses (Section 8.2.1)							
SBP, DBP, and MAP change from baseline to last record prior to change in BP medications ¹	ITT					Y			
Number of BP medications per subject by visit ¹	ITT	Y							
CFB in number of BP medications per subject by visit ¹	ITT					Y			
Number (%) of subjects who had no change, an increase or a decrease in dosage or number of BP medications from baseline by visit ¹	ITT	Y							
Lipid Parameters									
Lipid parameters by visit (TC, LDL-C, HDL-C)	ITT	Y	Y			Y			

NOTES :

- T = Table, F = Figure, L = Listing, Y = Yes display generated.
- Summary = Represents TFL related to any summaries (i.e. descriptive statistics) of the observed raw data.
- Individual = Represents FL related to any displays of individual subject observed raw data.

[1]: Summary will include on-treatment BP values or BP medications taken while the subject was on treatment only.

8.2.2.2. Planned Exploratory Safety Display Details

Blood Pressure

The last on-treatment BP parameter change from baseline value (SBP, DBP, and MAP) recorded prior to the first change in BP medications will be summarized using mean, standard deviation, minimum, P25, median, P75, and maximum by treatment group. The first change in blood pressure medication occurs at the earliest time a new anti-hypertensive medication is administered or if the dose or frequency of an existing blood pressure medication is changed for any reason (increased, decreased, discontinued, or switched to another agent) in any anti-hypertensive medication, except medication records with frequencies of “Once only” and “PRN.”

Number of BP medications per subject while the subject was on treatment will be summarized using mean, standard deviation, minimum, P25, median, P75, and maximum for each scheduled visit by treatment group. Number of BP medications for each subject at baseline is defined as the number of medications taken on the day before randomized treatment start date. For end of treatment, it is defined as the number of medications taken on last non-zero dose date + 1 day. The number of BP medications at all other nominal visits is defined as the number of medications taken on the day of the visit. Medication records with frequencies of “Once only” and “PRN” will be excluded from this summary.

Change from baseline in the number of BP medications per subject while the subject was on treatment will be summarized using mean, standard deviation, minimum, P25, median, P75, and maximum for each scheduled visit by treatment group. The number of BP medications at baseline, end of treatment and all other nominal visits will be defined as described in the previous paragraph. Medication records with frequencies of “Once only” and “PRN” will be excluded from this summary.

Additionally, the number and percentage of subjects who had no change, at least one change, an increase, a decrease or a switch in the dosage or number of BP medications from baseline while the subject was on treatment will be summarized for each scheduled post-baseline visit by treatment group (see Section 10.6.4 for details of classifying BP medication changes). Medication records with frequencies of “Once only” and “PRN” will be excluded from this summary.

Cumulative number of changes in on-treatment BP medications from baseline to Week 52 will be summarized by treatment group. For all records except with frequencies “Once only” and “PRN,” the cumulative number of changes will be summarized using mean, standard deviation, minimum, P25, median, P75, and maximum. The number of percentage of subjects with no change and at least one medication change will be displayed excluding “Once only” and “PRN” records. For subjects with at least one change, the number and percentage of subjects for each reason (increase, decrease, and switch) will be displayed (see Section 10.6.4 for details of counting BP medication cumulative changes) by treatment group. Number and percentage of subjects for each reason of BP medication change will be displayed by treatment group. Cumulative number of changes in on-treatment BP medication from baseline to Week 52 for “Once only” records only will be summarized using mean, standard deviation, minimum, P25,

CONFIDENTIAL

201410

median, P75, and maximum (see Section 10.6.4 for details of counting BP medication cumulative changes) by treatment group.

Number and percentage of subjects with at least one PRN record at baseline and on-treatment BP medication during the period from randomized treatment start date to Week 52 will be displayed by treatment group.

Number and percentage of subjects with any BP medication taken at baseline (the day before randomized treatment start date) and any on-treatment BP medication during the period from randomized treatment start date to Week 52 will be displayed by treatment group.

Lipid Parameters

Lipid parameter values for this study include total cholesterol, LDL-C (direct) and HDL-C. These values are collected according to the schedule outlined in the Time and Events table (see Section 10.2.1). Lipid parameter values follow the derivation guidelines for laboratory values outlined in Section 10.6.4. The summaries described below will include summaries in both SI units and conventional units for each of the lipid parameters and will summarize log-transformed values.

Total cholesterol, LDL-C (direct), and HDL-C on-treatment values will be summarized using geometric mean, CV, minimum, P25, median, P75, and maximum for each scheduled visit by treatment group.

Percent change from baseline in log-transformed on-treatment total cholesterol, LDL-C (direct), and HDL-C values will be summarized using percent change geometric mean, 95% confidence interval, minimum, P25, median, P75, and maximum for each scheduled visit by treatment group.

8.2.2.3. Overview of Exploratory Cardiovascular Safety Analysis

Table 10 provides an overview of exploratory cardiovascular safety analyses.

Table 10 Overview of Exploratory Cardiovascular Safety Analyses

Endpoint ¹	Analysis Population	Absolute						
		Stats Analysis			Summary		Individual	
		T	F	L	T	F	F	L
MACE	ITT	Y			Y	Y		Y
MACE or a thromboembolic event	ITT	Y			Y			
MACE or hospitalization for HF	ITT	Y			Y			
All-cause mortality	ITT	Y			Y			Y
CV mortality	ITT	Y			Y			
MI (fatal and non-fatal)	ITT	Y			Y			
Stroke (fatal and non-fatal)	ITT	Y			Y			

CONFIDENTIAL

201410

Endpoint ¹	Analysis Population	Absolute						
		Stats Analysis			Summary		Individual	
		T	F	L	T	F	F	L
CV mortality or non-fatal MI	ITT	Y			Y			
All-cause hospitalization	ITT	Y			Y			

NOTES :

- T = Table, F = Figure, L = Listing, Y = Yes display generated.
- Stats Analysis = Represents TFL related to any formal statistical analyses (i.e. modelling) conducted.
- Summary = Represents TFL related to any summaries (i.e. descriptive statistics) of the observed raw data.
- Individual = Represents FL related to any displays of individual subject observed raw data.

^[1]Adjudicated events used where available.

8.2.2.4. Planned Exploratory Cardiovascular Safety Analysis Details

Exploratory CV Safety Analyses
Endpoint(s)¹:

 • MACE (all-cause mortality, non-fatal MI, or non-fatal stroke) • MACE or a thromboembolic event • MACE or hospitalization for HF • All-cause mortality • CV mortality • MI (fatal and non-fatal) • Stroke (fatal and non-fatal) • CV mortality or non-fatal MI • All-cause hospitalization
Model Specification

 • For all exploratory CV endpoints, confidence intervals for the rate per 100 person-years will be reported. For within-group rates, the 95% CI will be obtained using an exact Poisson method. For difference in rates between treatments, the two-sided 95% CI will be constructed with a normal approximation using Walds' method [Liu, 2006]. • • For MACE endpoint, the calculation of time-to-event or censoring is described in further detail in Section 10.6.4.1. • First occurrence of adjudicated MACE for a subject is defined as the first adjudicated event, determined by the event date, which is indicated as all-cause mortality, non-fatal MI or non-fatal stroke with further details in Section 10.6.4.1. • For those endpoints or components of endpoints intended to go through the adjudication process, only the adjudicated results will be used.
Model Results Presentation

 • A summary of the number and percentage of subjects having first-occurrence MACE will be provided by treatment group. The number and percentage of the types of events that make up the first occurrence of MACE will also be provided by treatment group. This summary table will be repeated for MACE plus thromboembolic events, for MACE plus hospitalization for heart failure and for MACE plus thromboembolic events or hospitalization for CHF.

CONFIDENTIAL

201410

Exploratory CV Safety Analyses

- A summary of all MACE including the number and percentage of subjects and number of events (including first and subsequent MACE) by type of event will be provided by treatment group.
- A summary of the number and percentage of subjects having first-occurrence adjudicated COVID-19 MACE will be provided by treatment group. The number and percentage of the types of events that make up the first occurrence of adjudicated COVID-19 MACE will also be provided by treatment group.
- Summaries of adjudication details of all-cause mortality will include the number and percentage of subjects by cause of death.
- Summaries of adjudication details of MI will include the number and percentage of events by outcome of MI (fatal or non-fatal), type of MI, increased cardiac markers (y/n), ST segment classification [ST-elevation myocardial infarction (STEMI), non-ST-elevation myocardial infarction (NSTEMI), ECG not interpretable, ECG not available], and Q wave classification (Q wave MI, Non Q wave MI, ECG not interpretable, ECG not available).
- Summaries of adjudication details of stroke will include the number and percentage of events by outcome of stroke (fatal or non-fatal), type of stroke (ischemic, hemorrhagic, or undetermined) and ischemic details (with/without hemorrhagic transformation) and location if hemorrhagic (intraparenchymal, intraventricular, subarachnoid, retinal, unknown location).
- Summaries of adjudication details of heart failure will include the number of events by type: hospitalization for heart failure, heart failure requiring urgent ER/ED visit, heart failure requiring urgent office/practice visit, and fatal heart failure events identified by cause of death only.
- Summaries of adjudication details of thromboembolic events will include the number and percentage of events by type of thromboembolic event (DVT, PE, VAT).
 - Summaries of PEs will include outcome of PE (fatal or non-fatal).
 - Summaries of VATs will include type of VAT (AV fistula, AV graft, central venous catheter, other), method of diagnosis (ultrasound/Doppler, AV imaging, CVC imaging, other), and treatment (thrombolytic therapy, thrombectomy, angioplasty, stent, surgical intervention, not specified).
- A summary of adjudicated exploratory CV endpoints above (except all-cause hospitalization) will be provided to include the number and percentage of subjects and the number of events for each endpoint.
- The model results presentation for the endpoints above (except all –cause hospitalization) will be provided to include within-group incidence rates per 100 person-years (along with two-sided 95% CI), and difference in rates between treatments (along with two-sided 95% CI), For composite endpoints, the number and percentage of the type of first occurrence will be provided by treatment group.
- A summary of all-cause hospitalization will be provided by treatment group including summaries of the number of hospitalizations per subject, average length of stay per hospitalization and primary diagnosis at discharge by system organ class and lower level term.
- Time from Randomization to first occurrence of adjudicated MACE event or end of trial will be evaluated using Kaplan-Meier (KM) methodology and displayed graphically for the comparison of daprodustat vs. darbepoetin alfa.
- • Summary of concordance between events referred for adjudication and adjudicated endpoint events (Positively Adjudicated or Negatively Adjudicated) will be presented.

CONFIDENTIAL

201410

Exploratory CV Safety Analyses

 • A listing of all MACE events occurring during the study will be provided and will include treatment, site ID, unique subject ID, select demographic information, event type, event date, and study day. • A listing of all all-cause mortality events that occur during the study will be provided. This listing will include treatment, site ID, unique subject ID, select demographic information, event date, study day, and cause of death.

^[1] Adjudicated events used where available.

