9.4.4.1. Exploratory Cardiovascular Safety Analysis

This study is not designed or sufficiently powered for formal statistical analyses to assess cardiovascular safety. With fewer than 80 first MACE (defined as all-cause mortality, non-fatal MI, or non-fatal stroke) expected to occur during the trial, incidence rates and two-sided 95% CIs will be computed for the following mortality and CV composite or component endpoints: 1) MACE; 2) MACE or a thromboembolic event (vascular access thrombosis, a symptomatic deep vein thrombosis or a symptomatic pulmonary embolism); 3) MACE or hospitalization for heart failure; 4) all cause mortality; 5) CV mortality; 6) MI (fatal and non-fatal); 7) stroke (fatal and non-fatal); 8) CV mortality or non-fatal MI; 9) all cause hospitalization.

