Hospitalization for Heart Failure	
Systolic heart failure, Diastolic heart failure, Heart failure - unspecified type
 
Additional criteria: If admission/discharge times are non-missing, at least one of the following must be true (1-3):
 
 1. Time in hospital is ≥ 24 hours 2. Time in ED/ER is ≥ 24 hours 3. Consecutive time in hospital + time in ED/ER is ≥ 24 hours 
Or if admission/discharge times are missing, then at least one of the following must be true (4-6):
 
 4. Change in calendar date between hospital admission and discharge 5. Change in calendar date between ED/ER admission and discharge 6. Change in calendar date between consecutive hospital and ED/ER admission and discharge
Thromboembolic Event (DVT, PE, VAT)	Deep Vein Thrombosis (DVT), Pulmonary Embolism (PE), Vascular Access Thrombosis
All-cause mortality	Any death record
CV mortality	Any Cardiovascular primary cause of death
Non-CV mortality	Any Non-Cardiovascular primary cause of death
All-cause Hospitalization	

 ● All-cause hospitalization events are defined to be hospital admissions recorded on the Hospitalization eCRF form with a hospitalization duration ≥ 24 hours. ● Hospitalization rate (per year) across the study = number of all-cause hospitalization events / [follow-up time (days) / 365.25]. 	

CONFIDENTIAL

201410

CV Safety Endpoints
General Definitions

 • Time to event (days) = date of event – randomization date +1 • Censored time (days) = censoring date – randomization date + 1

 • First event person years = (cumulative total time to first event for subjects who have the event + cumulative total of censoring time for subjects without the event) / 365.25 • First event incidence rate (per 100 person years) = (100 * number of subjects with at least 1 event) / first event person years • First event absolute rate difference (per 100 person years) = daprodustat incidence rate (per 100 person years) – darbepoetin alfa incidence rate (per 100 person years)

Evaluation Time Periods for CV Endpoints
Time Period for Follow-up of Cardiovascular Endpoints

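### The SAP leaves all-cause hospitalization out of its rate and confidence-interval results, contrary to the protocol and its own model specification, and does not say which hospitalization rate would carry the interval

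*SAP*

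**What the plan says.** Protocol 9.4.4.1 (Exploratory Cardiovascular Safety Analysis) states that "incidence rates and two-sided 95% CIs will be computed for the following mortality and CV composite or component endpoints", and its list ends with "9) all cause hospitalization". Protocol 9.3.1 groups hospitalizations with mortality and MACE as time-to-event endpoints to be analysed in the ITT population.

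SAP 8.2.2.3, Table 10, marks all-cause hospitalization for a statistical analysis table as well as a descriptive one. SAP 8.2.2.4 lists it among the endpoints, and the model specification there makes no exception: "For all exploratory CV endpoints, confidence intervals for the rate per 100 person-years will be reported". The methods follow: "For within-group rates, the 95% CI will be obtained using an exact Poisson method", and "For difference in rates between treatments, the two-sided 95% CI will be constructed with a normal approximation using Walds' method".

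The results presentation in the same section departs from this: "The model results presentation for the endpoints above (except all –cause hospitalization) will be provided to include within-group incidence rates per 100 person-years". A matching exception removes hospitalization from the table of subject and event counts. What it keeps is descriptive: "A summary of all-cause hospitalization will be provided by treatment group including summaries of the number of hospitalizations per subject", along with length of stay and discharge diagnosis.

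SAP 10.6.4.1 holds two rates that could apply. One is specific to this endpoint: "Hospitalization rate (per year) across the study = number of all-cause hospitalization events", divided by follow-up in years. The other is the general first-event incidence rate per 100 person-years, which counts each subject at most once. The same section dates a hospitalization by its admission date.

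**The concern.** A programmer cannot satisfy Table 10, the model specification and the results presentation together. Following the results presentation means that a rate and CI required by the protocol are never produced. The departure is silent: SAP 2.1, Table 1, which records changes to the protocol-defined analysis, has no entry for it.

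The second gap appears as soon as the first is closed. Someone restoring the promised CI must choose between two rates with different numerators, and the text does not choose. The choice matters because a Poisson interval treats events as independent. That is reasonable when each subject contributes at most one event, but not when the same subjects are admitted repeatedly.

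**Working it through.** **Step 1. The texts side by side.**

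| Place | Rate and 95% CI for all-cause hospitalization? |
|---|---|
| Protocol 9.4.4.1, item 9 | Required |
| SAP 8.2.2.3, Table 10 | Statistical analysis table marked |
| SAP 8.2.2.4, model specification | Promised for every exploratory CV endpoint |
| SAP 8.2.2.4, results presentation | Excluded, from counts and from rates, differences and CIs |
| SAP 2.1, Table 1 | Exclusion not declared as a change |

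Three places call for the result, one removes it, and the change log does not mention the removal. This needs no assumption.

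**Step 2. Which rate would carry the CI?**

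- First-event rate (SAP 10.6.4.1): 100 × subjects with at least one event / first-event person-years. Person-years run from randomization to the first event, or to censoring. With the admission date as event date, it is fully defined for hospitalization.
- Hospitalization-specific rate (SAP 10.6.4.1): all admissions of at least 24 hours / (follow-up days / 365.25). Repeat admissions count, the unit is per year, and no CI is attached.

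The model specification attaches its CIs to rates per 100 person-years, which is the unit of the first-event rate. That favours the first-event reading, as does the time-to-event grouping in Protocol 9.3.1. The SAP does not say so.

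**Step 3. What depends on the choice (illustration only).** The documents give no admission rate and no dispersion, so there is no plan figure to reproduce. Inputs from the documents: 150 subjects per arm (Protocol 9.2.1) and 52 weeks of treatment, 364 / 365.25 = 1.00 year. Assumed: 0.5 to 2.0 admissions per person-year (μ) and negative binomial dispersion k from 0 to 2.

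If admissions per subject have mean μ and variance μ + kμ², the variance-to-mean ratio is 1 + kμ. A Poisson interval takes this as 1, so a valid interval must be wider by √(1 + kμ). Approximate coverage of the nominal 95% interval is 2Φ(1.96/√(1 + kμ)) − 1. For μ = 1.0 and k = 1 the ratio is 2, the width factor is 1.41, and coverage is 2Φ(1.386) − 1 = 83%.

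A simulation of 20,000 arms of 150 subjects, each followed for 1.0 year, gave these coverages. The Wald difference used 10,000 pairs of arms.

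| μ | k | Width factor | Exact Poisson, all admissions | Wald difference, all admissions | Exact Poisson, first event |
|---|---|---|---|---|---|
| 0.5 | 0.25 | 1.06 | 93.5% | 93.5% | 95.4% |
| 1.0 | 0 | 1.00 | 95.4% | 95.0% | 95.5% |
| 1.0 | 0.25 | 1.12 | 92.4% | 92.5% | 95.2% |
| 1.0 | 0.5 | 1.22 | 90.0% | 89.2% | 94.7% |
| 1.0 | 1 | 1.41 | 84.9% | 83.4% | 94.9% |
| 1.0 | 2 | 1.73 | 74.8% | 73.9% | 94.4% |
| 2.0 | 2 | 2.24 | 62.2% | 61.8% | 93.0% |

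Over the whole grid, the exact Poisson interval on the first-event rate covered 93.0% to 95.8%. The Wald interval for a first-event rate difference was not simulated.

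**The case against.** The strongest reply is that little is lost. Hospitalization is not dropped: a by-arm summary of admissions, length of stay and diagnosis remains. The analysis is exploratory, and Protocol 9.4.4.1 itself says the trial was neither designed nor powered to assess cardiovascular safety formally. The protocol asks for rates and CIs only; the between-arm difference is the SAP's addition. Hospitalization is also not among the events sent for adjudication (Protocol 7.4.1), which may explain why it was left out of a table of adjudicated counts. All of this stands, and it limits the consequence. It does not remove the contradiction: the second exception covers rates and CIs, and a descriptive summary is not what the protocol requires.

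A reader might go further and infer that the SAP's only hospitalization rate counts repeat admissions, and that the SAP prescribes an exact Poisson interval for it, with coverage of about 67% to 83%. The documents do not support this. The general first-event rate stands in the same section and can be applied using the admission date. No text attaches the Poisson interval to the all-admissions rate, and the units differ. That rate's denominator is not described as cumulative, so it may be only a per-subject descriptive quantity. The 67% to 83% range comes from the approximate formula with assumed rates of 1.0 to 1.5 per year and k of 1 to 2. Milder clustering gives far less: simulated coverage is 92.4% at a rate of 1.0 and k = 0.25.

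**Conclusion.** The point holds as a conflict between documents and within the SAP. A rate with a 95% CI for all-cause hospitalization is required by the protocol, promised twice in the SAP, excluded in the results presentation, and not declared as a change. The SAP also leaves open which of two rates would receive the CI. Neither statement rests on an assumption.

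The size is one omitted exploratory safety result. Too narrow an interval is a conditional risk: it arises only if the Poisson method is put on all admissions and admissions cluster within subjects. How large it would be cannot be derived from the documents, so the coverage figures above are illustrative. The primary analysis, the principal secondary test and type I error are unaffected. The point should be settled before unblinding, because a choice between the two rates made with the data in view would be open to question.

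**What to change.** 1. In the SAP 8.2.2.4 results presentation, delete both exceptions for all-cause hospitalization. In the counts table, label its row as taken from the Hospitalization eCRF form, since it is not adjudicated.
2. State that the rate carrying the CI is the first-hospitalization incidence rate per 100 person-years, using the first-event formula in SAP 10.6.4.1 with the admission date as event date. Report it with the exact Poisson within-group CI and the Wald CI for the rate difference.
3. Label the per-year all-admissions rate in SAP 10.6.4.1 as descriptive. If a CI is wanted for it, do not use the Poisson interval. Use the negative binomial model that SAP 8.2.1.2 applies to BP exacerbations, with log follow-up time as the offset in place of log time on treatment.
4. If the exclusion was intended, enter it in SAP Table 1 with a reason.

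The cost of items 1 and 2 is a few lines of SAP text and one row in each of two planned tables, with no new data. Item 3 adds one model, and only if a CI on all admissions is wanted.
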